### **11.1. Questionnaires**

At Visit 1 (Screening) before completing the daily WI-NRS for Day -14, subjects will receive training on how to respond to questionnaires. Sites will review the responses from each subject at least twice a week to ensure proper compliance.

#### **11.1.1. Worst Itch Numeric Rating Scale (WI-NRS)**

Subjects will be asked to rate the severity of their worst level of itching in the past 24 hours in the morning, and at the same time of day, using the WI-NRS. The WI-NRS is an 11-point scale ranging from 0 (No Itching) to 10 (Worst Itching Imaginable) ([Phan 2012](#)) and requires approximately 1 minute to complete. Higher scores indicate greater itch severity. Itching severity scores collected via the WI-NRS have been categorized in the literature as mild (<4), moderate ( $\geq 4$  to <7), or severe ( $\geq 7$ ) ([Fishbane 2020](#), [Hirschfield 2020](#), [Levy 2020](#), [Stander 2020](#)). An example of the WI-NRS is included in [Appendix B](#).

Subjects will be instructed to complete the WI-NRS daily, in the morning, and at the same time of day, beginning at Day -14 to the Follow-Up Visit. For days that coincide with a study visit (for Visit 2 and beyond), the WI-NRS is to be completed before the visit.

The WI-NRS scores from Day -7 through Day -1 will be averaged together to confirm compliance and determine subject eligibility for continued participation regarding pruritus sensation. The average WI-NRS score using the daily values from the week before the first dose of study drug (Visit 2 [Day 1]) will serve as the baseline score. The 7 daily WI-NRS scores prior to Visit 6 (Week 6) will be averaged together for primary endpoint analyses. Data from at least 4 of the 7 days for each week are required to be considered an acceptable profile.

#### **11.1.2. 5-D Itch Scale**

[figure not shown]
The 5-D Itch Scale was developed as a brief but multidimensional questionnaire designed for pruritus that measures changes over time (Elman 2010). The 5 dimensions are degree, duration, direction, disability, and distribution. It requires approximately 1 to 2 minutes to complete, and scores can range between 5 (no pruritus) and 25 (most severe pruritus). The scores of each of the 5 domains are achieved separately and then summed together to obtain a total 5-D score. An example of the 5-D Itch Scale is included in [Appendix C](#).

#### **11.1.3. Patient Global Impression of Severity (PGI-S)**

The PGI-S was validated in women with stress urinary incontinence, but may be used to rate the severity of other specific conditions (Yalcin 2003). For this questionnaire, the specific condition to be rated is pruritus. Subjects will be asked to rate the severity of their pruritus in the past 7 days using a 4-point scale from None to Severe. The PGI-S requires less than 1 minute to complete. An example of the PGI-S is included in [Appendix D](#).

#### **11.1.4. Patient Global Impression of Change (PGI-C)**

Subjects will be asked to rate their impression of overall change in pruritus in the past 7 days compared to before they started taking study drug using the PGI-C. The PGI-C is a 7-point scale ranging from Much Improved to Much Worse and requires approximately 1 minute to complete (Guy 1976). Higher scores indicate less improvement in pruritus. An example of the PGI-C is included in [Appendix E](#).

### **11.2. Blood and Urine Sampling for Pharmacodynamic Assessments**

Blood samples for genotyping (optional) and pruritus-related biomarkers (bile acids and heme metabolites) and blood and urine samples for future analysis will be assessed. Samples for genotyping and future analysis may be stored for up to 10 years after completion of the study.

### **11.3. Blood and Urine Sampling for Analysis of Kidney-Related Biomarkers**

Blood will be collected for analysis of kidney-related biomarkers such as cystatin-C and neutrophil gelatinase-associated lipocalin.

Urine will be collected for analysis of kidney-related biomarkers such as clusterin, cystatin-C, kidney injury molecule-1, N-acetyl- $\beta$ -D-glucosaminidase, neutrophil gelatinase-associated lipocalin, and osteopontin.

### **11.4. Height**

Height will be measured with no shoes.

## **12. SAFETY ASSESSMENTS**

Safety evaluations, including AEs, concomitant medications, medical history, vital signs, physical examinations, standard 12-lead ECGs, laboratory evaluations of safety, and disease-specific assessments (Partial Mayo Score for subjects with UC and CDAI for subjects with CD) will be performed as indicated in the Schedule of Assessments ([Appendix A](#)).

For the decentralized model, the Investigator may require the subject to have an in-person consultation with a physician after virtually conducting safety assessments, if deemed necessary.

## 12.1. Adverse Events

### 12.1.1. Definition of an Adverse Event

An AE is defined as any untoward medical occurrence in a subject administered a pharmaceutical product and which does not necessarily have a causal relationship with this treatment. An AE can therefore be any unfavorable or unintended sign (including a clinically significant abnormal laboratory finding), symptom, or disease temporally associated with the use of a medicinal (investigational) product.

Medical conditions present at baseline that worsen in severity or frequency after exposure to study drug are considered treatment-emergent AEs (TEAEs). Planned hospital admissions or surgical procedures for an illness or a disease that existed before administration of study drug, and for which the condition has not worsened since starting study drug, are not to be considered TEAEs/treatment-emergent serious AEs (SAEs). Events with emergency room visits that are less than 24 hours will also not be considered SAEs unless they meet one of the criteria listed in [Section 12.2.1](#).

Clinically significant abnormal laboratory tests, 12-lead ECG assessments, or vital sign results may, in the opinion of the Investigator, constitute an AE. However, whenever possible, the underlying diagnosis should be listed in lieu of associated abnormal results. Abnormalities deemed not clinically significant by the Investigator should not be reported as AEs.

### 12.1.2. Determining Severity of Adverse Events

AEs must be graded for severity (ie, intensity) using CTCAE, version 5.0 ([HHS 2017](#)). A severity category of mild, moderate, severe, life-threatening, or death, as defined below, must be entered on the AE eCRF. It should be noted that the term “severe” used to grade intensity is not synonymous with the term “serious”. The assessment of severity is made regardless of the relationship to study drug or of the seriousness of the AE. When reporting AEs, reference should be made to the CTCAE manual for guidance on appropriate grading.

- |          |  |
|----------|--|
| Grade 1: | Mild; asymptomatic or mild symptoms; clinical or diagnostic observations only; intervention not indicated.   |
| Grade 2: | Moderate; minimal, local or noninvasive intervention indicated; limiting age-appropriate instrumental activities of daily living (eg, preparing meals, shopping for groceries or clothes, using the telephone, and managing money).  |
| Grade 3: | Severe or medically significant, but not immediately life-threatening; hospitalization or prolongation of hospitalization indicated; disabling, limiting self-care activities of daily life (eg, bathing, dressing and undressing, feeding self, using the toilet, taking medications, and not bedridden). |
| Grade 4: | Life-threatening consequences, urgent intervention indicated.  |
| Grade 5: | Death related to AE.   |

All CTCAE Grade 3 or higher must be reported to the Sponsor or designee using the SAE/AESI/Grade 3+ Report Form, according to the timelines described for SAEs in [Section 12.2.2](#).

### 12.1.3. Determining Causality of Adverse Events

Causality refers to the relationship of the event to the study drug (EP547 or placebo). The Investigator will assess the causality of the event according to the following criteria:

- **Not related** – A reaction for which sufficient data exist to indicate that the etiology is unrelated to the study drug.
- **Related** – A reaction that follows a reasonable temporal sequence from administration of study drug; that follows a known or expected response pattern to the study drug, which may or may not reasonably have been produced by a number of other factors including underlying disease, complications, concomitant drugs, or concurrent treatments; and/or that could not be reasonably explained by other factors such as underlying disease, complications, concomitant drugs, or concurrent treatments; and/or disappears or decreases on cessation or reduction in study drug dose; and/or reappears or worsens when the study drug is administered.

### 12.1.4. Recording Adverse Events

All AEs must be recorded in the source documents and in the eCRFs provided by the Sponsor from the signing of the Informed Consent Form (ICF) until the end of study participation. AEs will be assessed for likelihood of causal relationship to the study drug (EP547 or placebo) and severity.

The new onset of signs, symptoms, or other findings that occur before signing of the ICF will be captured as medical history ([Section 12.4](#)).

#### 12.1.4.1. Special Instructions for Recording Adverse Events in the eCRF

##### Diagnosis versus Signs and Symptoms

If a diagnosis is known at the time of reporting, this should be recorded in the eCRF rather than the individual signs and symptoms (eg, record only hepatitis rather than elevated transaminases, bilirubin, and jaundice). However, if a constellation of signs and/or symptoms cannot be medically characterized as a single diagnosis or syndrome at the time of reporting, each individual event should be recorded as an SAE or AE on the eCRF. If a diagnosis is subsequently established, it should be reported as follow-up and should replace the individual signs and/or symptoms as the event term on the eCRF, unless the signs/symptoms are clinically significant.

##### Adverse Events Occurring Secondary to Other Events

In general, AEs occurring secondary to other events (eg, clinical sequelae or a cascade of events) should be identified by their primary cause. For example, if severe vomiting is known to result in dehydration, it is sufficient to record only vomiting as an AE on the eCRF. However, medically significant AEs occurring secondary to an initiating event that are separated in time should be recorded as independent events on the eCRF. For example, if severe vomiting leads to acute renal failure, both events should be recorded on the eCRF.

### **Persistent or Recurrent Adverse Events**

A persistent AE is one that extends continuously, without resolution, between subject evaluation timepoints. Such events should only be recorded once on the eCRF. If a persistent AE becomes more severe or lessens in severity, it should be recorded as a new AE on the eCRF.

A recurrent AE is one that occurs and resolves between subject evaluation timepoints, and subsequently recurs. Each reoccurrence of an AE should be recorded on the eCRF.

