#### 4.5.3 Adverse Events

Treatment-emergent adverse events are defined as those AEs with onset after the first dose of study drug or existing events that worsened after the first dose during the study. Treatment-emergent AEs will be summarized by treatment group separately for each study treatment period and overall, within each study treatment period. An overall TEAE summary, incidence of TEAEs by system organ class and preferred term, and summary of the most frequently-occurring TEAEs will also be presented for both periods combined (i.e., overall study) for the Safety Analysis Set and the Open-Label Extension Analysis Set. Adverse events will be considered treatment-emergent relative to the study treatment period where the onset of the AE occurred; any TEAE that begins in the Double-Blind Treatment Period will be considered treatment-emergent in the Double-Blind Treatment Period only. The same logic is to be applied to the Open-Label Extension assessment; the Week 6 Study Drug Administration (On-site) entry will be considered the start of Open-Label Extension dosing for assessing treatmentemergence. Events reported with a partial onset date (e.g., month and year are reported but the day is missing) will be considered to be treatment-emergent in both treatment periods if it cannot be confirmed that the event onset was prior to the first dose of study drug for a specific treatment period based on the available date entries. Events with date and time present will be compared against the treatment start date and time to determine treatment-emergence.

Verbatim terms on case report forms will be mapped to preferred terms and system organ classes using MedDRA, version 25.0.

Summaries that are displayed by system organ class and preferred terms will be ordered by descending incidence of system organ class and preferred term within each system organ class. Summaries displayed by preferred term only will be ordered by descending incidence of preferred term. Inclusion criteria assessments for frequency-related summaries will be made separately for each study treatment period and study overall. Summaries of the following types will be presented:

- Overall summary of number of unique TEAEs and treatment-emergent SAEs and subject incidence of TEAEs meeting various criteria;
- Subject incidence of TEAEs by MedDRA system organ class and preferred term;

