- Subject incidence of the most frequently-occurring TEAEs (i.e., TEAEs occurring in ≥ 10% of the Safety Analysis Set or Open-Label Extension Analysis Set) by MedDRA preferred term;
- Subject incidence of TEAEs by CTCAE severity grade, MedDRA system organ class, and preferred term;

- Subject incidence of TEAEs by relationship to study drug, MedDRA system organ class, and preferred term;
- Subject incidence of TEAEs of Special Interest by MedDRA system organ class and preferred term;
- Subject incidence of the most frequently-occurring TEAEs related to study drug (i.e., related TEAEs occurring in ≥ 10% of the Safety Analysis Set or Open-Label Extension Analysis Set) by MedDRA preferred term;
- Subject incidence of CTCAE grade 3 or higher TEAEs related to study drug by MedDRA system organ class and preferred term; and
- Subject incidence of SAEs by MedDRA system organ class and preferred term.

A summary by safety subgroups of interest (type of cholestatic disease and baseline eGFR) described in Section 4.4.7.8 will be provided for the overall AE summary and subject incidence of TEAEs by MedDRA system organ class and preferred term for the Double-Blind Treatment Period, Open-Label Extension Period, and study overall.

At each level of summarization (e.g., any AE, system organ class, and preferred term), subjects experiencing more than one TEAE will be counted only once. In the summary of TEAEs by severity grade, subjects will be counted once at the highest severity reported at each level of summarization; in the summary of TEAEs by relationship, subjects will be counted once at the closest relationship to study drug. Related events include those reported as "Related" to study drug; events considered not related are those reported as "Not Related" to study drug.

Adverse event data will be presented in data listings by subject, treatment group, and event. Serious AEs and AEs leading to discontinuation of the study drug will be presented in separate data listings.

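### An AE record opened only because a persistent AE lessened can be counted as a new treatment-emergent event under the SAP's onset-date rule

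*Protocol*

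**What the plan says.** Protocol 12.1.4.1, under Persistent or Recurrent Adverse Events, treats a persistent event as continuous and unresolved, and adds: "If a persistent AE becomes more severe or lessens in severity, it should be recorded as a new AE on the eCRF". Recurrences after resolution are recorded separately. Under Protocol 12.1.4, recording begins at consent, so an event can already be open at the first dose.

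SAP 4.5.3 gives two alternative routes to treatment-emergence: "Treatment-emergent adverse events are defined as those AEs with onset after the first dose of study drug or existing events that worsened" after that dose. It then works by date: "Events with date and time present will be compared against the treatment start date and time to determine treatment-emergence". The period follows onset: "Adverse events will be considered treatment-emergent relative to the study treatment period where the onset of the AE occurred". It adds that "any TEAE that begins in the Double-Blind Treatment Period will be considered treatment-emergent in the Double-Blind Treatment Period only". For conditions that already exist, Protocol 12.1.1 and 14.9 also name worsening and nothing else.

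The planned tables include an "Overall summary of number of unique TEAEs and treatment-emergent SAEs"; the word unique is not defined. For incidence at each level, "subjects experiencing more than one TEAE will be counted only once". In the severity table, "subjects will be counted once at the highest severity reported at each level of summarization".

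SAP 4.5.3 also plans several AE tables over both periods combined. SAP 4.5.5 and 4.5.6.2 plan study-overall laboratory and ECG summaries. The general groupings in SAP 4.1.1 and 4.5 are by randomised arm plus all subjects combined.

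**The concern.** The protocol calls the follow-on record a new AE, and the SAP classifies an AE by its onset. Neither SAP 4.5.3 nor the protocol links a severity-change record to the event it continues, and the onset route has no carve-out for improvement. A programmer applying the text literally, with the new record dated at the grade change, would flag recovery as treatment-emergent. That contradicts the plan's own concept, under which an existing event becomes emergent by worsening.

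Two kinds of table are at stake. An event that began on placebo and merely eased during the extension could be listed as an event arising on open-label EP547. An event total could also rise because an AE got better gradually and not abruptly. The same emergence flag feeds the tables by severity, by relationship and of special-interest events, so a misclassified record carries through to those as well.

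**Working it through.** The plan states no figure here to reproduce. The check applies the rules to example records and then sizes one case.

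**Inputs.** Double-blind Days 1–42 and open-label Days 43–85 (Protocol Table 4); 29 randomised per arm, of whom 26 are expected to complete (Protocol 14.4, SAP 4.6). Assumptions: the follow-on record's onset is the date of the grade change; all 58 randomised subjects are dosed; 26 per arm enter the extension.

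**Step 1: apply the date rule.**

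| Course of one AE | Records | Literal date rule | Worsening-only concept |
|---|---|---|---|
| Grade 2 from Day −5, Grade 1 from Day 10 | 2 | second record is a double-blind TEAE | no TEAE |
| Starts Day 30, lessens Day 50 | 2 | one double-blind and one open-label TEAE | one double-blind TEAE |
| Grade 3 in the double-blind period, then Grade 2 and Grade 1 in the extension | 3 | one double-blind and two open-label records | one double-blind TEAE |

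In the second and third rows the double-blind-only rule does not clearly help. Taken as a new AE, the follow-on record does not begin in the double-blind period.

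**Step 2: what the counting rules absorb.** Subjects are counted once per level and at their highest grade. A step-down within one period, for an AE already counted there, therefore leaves incidence unchanged and adds only to event totals. A double-blind AE that eases in the extension is already present in the overall-study incidence table. Incidence changes only in a period-specific table, or for an AE open before the first dose, and only if the subject has no genuine TEAE at that level in that period.

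**Step 3: size of one case.**
- Double-blind, one arm: 1/29 = 3.4 points.
- Open-label, one arm: 1/26 = 3.8 points; both arms together, 1/52 = 1.9 points.
- The SAP's list of most frequent TEAEs uses a 10% threshold: 0.10 × 58 = 5.8 and 0.10 × 52 = 5.2, so six subjects are needed on either base. One false case could list a preferred term that has five genuine ones. This is an illustration, not a forecast.

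The documents give no rate of step-downs, so no expected number of cases can be calculated.

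**Step 4: the overall-study tables.** For a placebo-randomised completer, 43/85 = 50.6% of treatment days are on EP547. If 26 of 29 cross over and the other three contribute the full double-blind period, the share is 26 × 43 / (29 × 42 + 26 × 43) = 1118/2336 = 47.9%. With a 42-day extension it is 1092/2310 = 47.3%. About half of that column's time is therefore EP547 time. This follows from the crossover into open label; it does not measure an error.

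**The case against.** The best defence is that SAP 4.5.3 can be read benignly. It speaks of the onset of the AE, and the protocol regards a persistent AE as one continuous event, so the parent's onset could govern and the double-blind-only rule would then cover an event that eases later. The worsening route names worsening only, and unique suggests de-duplication. The onset date given to a severity-change record may be fixed in the eCRF design or completion guide, which are not among these documents. The screening route is narrow: findings before consent go to medical history, so the AE must arise after consent, be open at dosing and then drop a grade. All AEs are listed by subject, so records can be traced.

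Much of this stands and limits the size. It does not close the gap, because the protocol itself names the follow-on record a new AE, the onset route is a separate alternative without an exception, and unique is left to the programmer.

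Three stronger readings are tempting, and the documents do not support them:
- A reader might infer that the recording rule is the fault. It usefully preserves dated grade changes; what is missing is an analysis rule.
- A reader might infer that AE incidence is inflated generally. The once-per-subject rule prevents that.
- A reader might infer that the overall-study tables corrupt the EP547–placebo safety contrast. Double-blind tables are produced separately, open-label tables by randomised arm already isolate placebo-to-EP547 time, and no between-arm safety test is planned. The combined tables' exact column headings are not spelled out either.

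**Conclusion.** The point holds conditionally and is minor. As written, the onset-date rule can tabulate improvement as a treatment-emergent event, provided the follow-on record is dated at the grade change. That dating is the natural convention, but the documents do not state it. The effect on incidence is confined to AEs open at the first dose or carried into the extension, in subjects with no other TEAE at that level in that period: 3.4 or 3.8 points per case within an arm. The effect on the event count is wider but cannot be sized without a rate of step-downs. Nothing in the documents shows which arm would be affected more. Mixing of placebo-randomised subjects' time in the overall-study tables is a labelling matter only.

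**What to change.** In SAP 4.5.3, add:
- A record opened only because a persistent AE lessened is linked to its parent AE, keeps the parent's onset for treatment-emergence and period, is never itself a TEAE, and adds nothing to the unique-TEAE count. Define that count accordingly.
- A record whose grade exceeds that of the immediately preceding record, with the increase after the first dose, still counts as a worsened existing event. State which period it belongs to, and how that fits the double-blind-only rule. Compare with the preceding record and not with the grade just before the period began; otherwise a Grade 2 to 1 to 2 course would hide on-drug worsening.
- An AE that resolved and recurred remains a separate event.
- The link rests on the investigator's record or on a blinded review completed before unblinding. Preferred term and adjoining dates alone could merge true recurrences.

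As a secondary, presentational change, where overall-study tables are shown by randomised arm, label the columns EP547 then EP547 and placebo then EP547. State that only the double-blind tables support the EP547–placebo comparison. A descriptive any-EP547 column is optional, for AEs only. For DILI or creatinine criteria measured from the pre-double-blind baseline, it would attribute rises that began on placebo to EP547.

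The cost is slightly more SAP wording and programming, plus the blinded review where it is used. No new data are needed, and the protocol's recording rule stays as it is.
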